 17.9 Appendix 9- Analysis Templates for the Secondary Efficacy Endpoints Measured at
365±14 Days Following the First and last Infusion 90

Glossary of Abbreviations

Abbreviation	Definition
ACE	American College of Endocrinology
AE	Adverse Event
AIR _{glu}	Acute Insulin Response to glucose
ATG	Rabbit Anti-thymocyte Globulin
BMI	Body Mass Index
BG	Blood Glucose
BW	Body Weight
CGMS	Continuous Glucose Monitoring System [®]
CIT	Clinical Islet Transplantation
DDS	Diabetes Distress Scale
DI	Disposition Index
DSMB	Data Safety Monitoring Board
EQ-5D	European Quality of Life
FSIGT	Frequently-sampled Intravenous Glucose Tolerance
GFR	Glomerular Filtration Rate
HbA1c	Glycosylated Hemoglobin
HFS	Hypoglycemia Fear Scale
HLA	Histocompatibility Antigen
HSA	Human Serum Albumin

Statistical Analysis Plan

Abbreviation	Definition
IEQ	Islet Equivalents
ITT	Intent To Treat
LI	Lability Index
MAGE	Mean Amplitude of Glycemic Excursions
MCMC	Monte Carlo Markov Chain
MMTT	Mixed-meal Tolerance Test
NCI	National Cancer Institute
NIH	National Institutes of Health
OHS	Overall Health Status
PAID	Problem Areas in Diabetes
QOL	Quality of Life
SAE	Serious Adverse Event
SAP	Statistical Analysis Plan
SI	Insulin Sensitivity
SMC	Summary Mental Component
SPC	Summary Physical Component
T1D	Type 1 Diabetes
TCAE	Terminology Criteria for Adverse Events
ULN	Upper Limit of Normal

1. Introduction

Type 1 diabetes (T1D) afflicts nearly 2 million people in the United States, most of them children or young adults. Exogenous insulin, administered by multiple injections or by a continuous subcutaneous infusion from a wearable pump, allows long term survival in those who develop the disease, and most who are treated in this way will have a very good health-related quality of life (QOL). However, insulin therapy does not provide normal glycemic control, and long-term survivors commonly develop vascular complications such as diabetic retinopathy (the most common cause of adult blindness) and diabetic nephropathy (the most common indication for adult kidney transplantation). A small minority of individuals with T1D develop hypoglycemia unawareness, a condition that is life threatening, is associated with severe deterioration in QOL and activity restriction, and is not amenable to medical therapy.

The hope of achieving near-normal glucose control without hypoglycemia in T1D has provided the impetus for developing effective strategies for β -cell replacement via pancreas or isolated islet transplantation. Islet transplantation is accomplished by a procedure in which the islets are infused into the portal vein. While this procedure is not without risk, the procedural morbidity is much less than that of whole pancreas transplant.

While about 80% of whole pancreas transplant recipients will be insulin independent at one year after their transplant, less than 10% of 447 islet recipients transplanted between 1990 and 1999 achieved one year insulin independence. This was attributed to low engrafted islet mass combined with high metabolic demand imposed by glucocorticoids used to prevent rejection. In the year 2000, the group from Edmonton reported a series of 7 consecutive islet transplant recipients treated with islets from multiple donors and a glucocorticoid-free immunosuppressive regimen (Markmann, S, Huang, & al., 2003). These islet recipients were insulin free at follow-up ranging from 4.5 to 15 months. All of the recipients had experienced severe hypoglycemic episodes prior to transplant, and afterwards, none did. The efficacy of the Edmonton approach has now been confirmed by several other centers, and represents a major breakthrough in the field.

A Clinical Islet Transplantation (CIT) consortium has been formed to conduct a multicenter trial with the goal of providing strong scientific evidence that the rate of favorable outcome in transplanted subjects is high enough to justify the risks of the islet transplant procedure and the required immunosuppression.

This document briefly describes the study design and provides a detailed statistical analysis plan (SAP) for treatment efficacy and safety assessments. Details of all study aspects are given in the formal study protocol (CIT-06).

2. Study Design and Objectives

2.1 Study Design

This is a prospective, single-arm, multi-center study assessing the benefit of islet transplantation in type 1 diabetic (T1D) kidney transplant recipients. The participating centers will treat a total of 24 subjects.

2.2 Study Objective

The primary objective is to test the hypothesis that islet transplantation in patients with established kidney transplants leads to improved metabolic control as measured by serial HbA1c levels and a reduced occurrence of hypoglycemic events.

Secondary objectives of this study will assess whether successful islet transplantation leads to improved Quality of Life (QOL), improved metabolic control as determined by a wide variety of measurements and reduced risk of cardiovascular and renal complications from diabetes.

2.2.1 Selection of Subjects

Please see Section 3 of the CIT-06 protocol for subject inclusion and exclusion criteria.

2.2.2 Study Treatment Regimen

2.2.2.1 Investigational Agent: Allogeneic Islets

The investigational agent is the Purified Human Pancreatic Islet product. The final product is a sterile suspension of $\geq 70\%$ viable, $\geq 30\%$ pure, allogeneic human purified islets in 200 mL of transplant media containing 2.5% human serum albumin (HSA), 25 mM Hepes for administration by intraportal infusion. Each product lot may comprise up to 3 bags containing 200 mL each. The final product dose is $\geq 5,000$ islet equivalents (IEQ)/kg recipient body weight (BW) for the first infusion, and $\geq 4,000$ IEQ/kg recipient BW for subsequent infusions.

The transplant procedure involves infusion of the final product into a branch of the portal vein, which is accessed by percutaneous transhepatic cannulation using ultrasound guidance and fluoroscopic localization of the liver, or under direct visualization via a minilaparotomy.

2.2.2.2 Immunosuppression

For the first islet transplant, the study medication is administered concomitantly with a consensus regimen of immunosuppressive and anti-inflammatory medications that includes rabbit anti-

Statistical Analysis Plan

thymocyte globulin (Thymoglobulin[®]), Methylprednisolone (Solumedrol[®]), Basiliximab (Simulect[®]) (for subsequent transplants only), and Etanercept (Enbrel[®]).

2.3 Study Endpoints

2.3.1 Primary Endpoint

The primary endpoint for this study is the proportion of subjects with both an HbA1c $\leq 6.5\%$ and an absence of severe hypoglycemic events at 1 year after the *first* islet transplant or a reduction in HbA1c of at least 1 point and an absence of severe hypoglycemia at 1 year after the *first* islet transplant.

2.3.2 Secondary Endpoints

Because there are a large number of secondary endpoints, it is impractical to account for all multiple comparisons. However, a few secondary endpoints have been identified as **key** secondary endpoints. Analysis of these key secondary endpoints will account for the multiplicity of tests.

2.3.2.1 Key secondary endpoints

The target level for HbA1c chosen for this study is 6.5%. This value was chosen because it is the level recommended by the American College of Endocrinology. We have included achieving a HbA1c level of 7.0%, alone and as a composite with freedom from **severe hypoglycemic events** at 1 year after the first and last islet transplants, as secondary endpoints because they correspond to the American Diabetes Association recommendations and will be of interest to the medical community. In addition, the primary endpoint for the Islet Alone study (CIT-07) uses 7.0% for the HbA1c cut-off. Inclusion of this endpoint will allow direct comparison with the Islet Alone study.

The key secondary endpoints are the following:

At 365 ± 14 days after the *last* islet transplant (the primary at 365 days after the last transplant):

The proportion of subjects with both an HbA1c $\leq 6.5\%$ and an absence of severe hypoglycemic events from Day 28 to Day 365, or a reduction in HbA1c of 1 point and an absence of severe hypoglycemia from Day 28 to Day 365.

At 365 ± 14 days after the *first* islet transplant:

- The proportion of subjects with HbA1c $< 7.0\%$ and free of severe hypoglycemic events from Day 28 to Day 365.
- The proportion of subjects free of severe hypoglycemic events from Day 28 to Day 365.
- The proportion of subjects with HbA1c $< 7.0\%$.

Statistical Analysis Plan

- The proportion of subjects with $HbA1c \leq 6.5\%$.
- The proportion of subjects with a reduction in HbA1c of at least 1 point.
- The proportion of insulin-independent subjects.
- The change in Clarke score from baseline to Day 365.

2.3.2.2 Additional efficacy endpoints

Other secondary efficacy endpoints include measures at one year, two years, and three years after the first and/or after the last islet transplant.

One year (365 ± 14 days) after the last islet transplant:

- The proportion of subjects with $HbA1c < 7.0\%$ and free of severe hypoglycemic events from Day 28 to Day 365.
- The proportion of subjects free of severe hypoglycemic events from Day 28 to Day 365.
- The proportion of subjects with $HbA1c < 7.0\%$.
- The proportion of subjects with $HbA1c \leq 6.5\%$.
- The proportion of subjects with a reduction in HbA1c of at least 1 point.
- The proportion of insulin-independent subjects.
- The change in Clarke score from baseline to Day 365.

Two years (730 ± 14 days) after the first and after the last islet transplant:

- The proportion of subjects with an $HbA1c \leq 6.5\%$ AND free of severe hypoglycemic events from Day 28 to Day 730, or a reduction in HbA1c of 1 point and an absence of severe hypoglycemia from Day 28 to Day 730, inclusive.
- The proportion of subjects with $HbA1c < 7.0\%$ AND free of severe hypoglycemic events from Day 28 to Day 730.
- The proportion of subjects free of severe hypoglycemic events from Day 28 to Day 730.
- The proportion of subjects with $HbA1c < 7.0\%$.
- The proportion of subjects with $HbA1c \leq 6.5\%$.
- The proportion of subjects with a reduction in HbA1c of at least 1 point.
- The proportion of insulin-independent subjects.
- The change in Clarke score from baseline to Day 730.

Statistical Analysis Plan

Three years (1095±14 days) after the first and after the last islet transplant:

- The proportion of subjects with an HbA1c <7.0% AND free of severe hypoglycemic events from Day 28 to Day 1095, inclusive.
- The proportion of subjects with HbA1c ≤ 6.5% AND free of severe hypoglycemic events from Day 28 to Day 1095 or a reduction in HbA1c of 1 point and an absence of severe hypoglycemia from Day 28 to Day 1095.
- The proportion of subjects free of severe hypoglycemic events from Day 28 to Day 1095 after the last islet transplant.
- The proportion of subjects with HbA1c <7.0% at 1095 day after the last islet transplant.
- The proportion of subjects with HbA1c ≤6.5% at 1095 years after the last islet transplant.
- The proportion of subjects with a reduction in HbA1c of at least 1 point.
- The proportion of insulin-independent subjects at 1095 days.
- The change in Clarke score from baseline to Day 1095.

2.4 *Metabolic Measures*

Specific metabolic measures include the following:

At 75 ± 5 days following each islet transplant:

- Insulin independence

At one year (365 ± 14 days) following the first and the last islet transplant(s):

- Cardiovascular events [death, cerebrovascular accident (CVA), myocardial infarction (MI)], changes in carotid intima-medial thickness, atherogenic profile, and ratio of Apolipoprotein A1 and B
- Renal impact measures including renal allograft survival and function measured by serum creatinine (SCr) and urinary albumin creatinine ratio
- Number of severe hypoglycemic events
- The percent change from baseline insulin requirements
- HbA1c
- MAGE
- LI
- Clarke score [14]
- HYPO score

Statistical Analysis Plan

- Basal (fasting) and 90-min glucose and C-peptide (MMTT)
- β -score
- C-peptide/(glucose•creatinine) ratio
- AIR_{glu}, SI, and DI derived from the FSIGT test [5]
- Glucose variability and hypoglycemia duration derived from the CGMS®
- QOL, as defined in SAP section 3.6.5.
- The proportion of subjects receiving a second islet transplant
- The proportion of subjects receiving a third islet transplant
- Rate of favorable outcome at each center preparing islets (rate of subjects with an HbA1c $\leq 6.5\%$ and absence of severe hypoglycemic events from Day 28 to Day 1095, or reduction in HbA1c of 1 point and absence of severe hypoglycemia from Day 28 to Day 1095)

At two years (730 ± 14 days) and three years (1095 ± 14 days) after the last islet transplant:

- Cardiovascular events [death, cerebrovascular accident (CVA), myocardial infarction (MI)], changes in carotid intima-medial thickness, atherogenic profile, and ratio of Apolipoprotein A1 and B
- Renal impact measures including renal allograft survival and function measured by serum creatinine (SCr) and urinary albumin creatinine ratio
- The percent change from baseline insulin requirements.
- The number of severe hypoglycemic events
- HbA1c
- Clarke score
- Basal (fasting) and 90-min glucose and c-peptide (MMTT)
- β -score
- C-peptide: (glucose•creatinine) ratio
- AIR_{glu}, SI, and DI derived from the FSIGT test [5]
- CGMS
- QOL

2.5 *Quality of Life Variables*

In this study, five QOL measures are considered. Two scales are obtained from the SF36 questionnaire (version 2). These scales are the Summary Physical Component score (SPC) and the Summary Mental Component score (SMC). Additional QOL assessments include the Overall Health Status (OHS) measure based on the European Quality of Life (EQ-5D) instrument, the Diabetes Distress Scale (DDS), and the Hypoglycemia Fear Scale (HFS) scales.

The SF36 scales will be standardized to the US population. The EQ-5D OHS questionnaire provides two sub-scales: the Behavior subscale that is based on 10 questions and ranges from 0 to 40 and the Worry subscale that is based on 13 questions. The scale is computed as the sum of the responses to the 13 questions and ranges from 0 to 52. The DDS is based on 17 questions rated on a 6 point Likert scales and ranges from 17 to 102. The HFS has two subscales: the Behavior scale which ranges from 0 to 40 and the Worry scale that ranges from 0 to 52.

2.6 *Time to Event Outcomes*

Multiple time-to-event outcomes will also be studied. All events will be defined for the period from the first transplant to 1095 days after the last islet transplant.

- Time to death (all cause and also cardiac related) and time to cardiovascular events (death, CVA, MI)
- Time to $HbA1c \leq 6.5\%$
- Time to first severe hypoglycemia episode
- Time to $HbA1c$ decreasing by at least 1%
- Time to global treatment failure composite outcome measure defined as the time to the first occurrence of any of the following:
 - Death
 - Stroke
 - MI
 - Above the ankle amputation

All of the above will be ascertained from the SAE reports and will be adjudicated if an adjudication committee is available.

- Renal Failure (Any one of the following):
 - Initiation of dialysis; or
 - Renal transplantation
- Blindness: Visual acuity of 20/200 in both eyes.
- Poor diabetes control (if any of the following occur):
 - $HbA1c > 9\%$ and reduced less than 1% below the entry level, found 6 months or more following the first transplant and confirmed on repeat examination at least

Statistical Analysis Plan

30 days and no more than 60 days later. If confirmed, failure is the time of the initial draw;

- Three consecutive monthly HbA1c values greater than the baseline value, with the first one being 6 months or more following the first transplant; or
- Occurrence of two severe hypoglycemic events (requiring assistance from another person) within a three month period. Failure will occur at the time of the second hypoglycemic event.

2.7 Safety endpoints

Safety endpoints include the following:

At 75 ± 5 days following each transplant, at 365 ± 14 days following the first and last islet transplant(s), at 730 ± 14 days following the last islet transplant, and at 1095 ± 14 days following the last islet transplant:

- The incidence and severity of adverse events (AEs) related to the islet transplant procedure, including: bleeding (>2 g/dL decrease in hemoglobin concentration); segmental portal vein thrombosis; biliary puncture; wound complication (infection or subsequent hernia); and increased transaminase levels >5 times upper limit of normal (ULN)
- The incidence and severity of AEs related to the immunosuppression including: allergy; reduction in glomerular filtration rate (GFR); increase in urinary albumin excretion; addition or intensification of anti-hypertensive therapy; addition or intensification of anti-hyperlipidemic therapy; oral ulcers; lower extremity edema; gastrointestinal toxicity; neutropenia, anemia, or thrombocytopenia; viral, bacterial, or fungal infections; and benign or malignant neoplasms
- The incidence of change in the immunosuppression drug regimen
- The incidence of immune sensitization defined by presence of anti-HLA (histocompatibility antigen) antibodies absent prior to transplantation
- The proportion of subjects who withdraw from study treatment due to an organ transplant

At 365 ± 14 days following the first and last islet transplant and at 1095 days following the last islet transplant:

- The incidence of worsening retinopathy as assessed by change in retinal photography

3. Subgroup Analysis

A Subject may enter the study because she/he is having severe hypoglycemic events that require assistance or because she/he is unable to reduce HbA1c level to below 7.5% on Intensive Insulin

Statistical Analysis Plan

Therapy (see inclusion criterion 7 in the protocol). The latter group may be very small. However, if there are at least 6 subjects in each group, we will perform subgroup analyses that examine these two subgroups separately. Analyses will include all primary and secondary outcome measures and use the same analysis strategies that were used for those measures. Please note that power for these analyses will be very small but the results may lead to a better understanding of the mechanisms of outcome.

4. Sample Size and Power Calculations

Sample sizes were calculated for the primary endpoint as a composite dichotomous variable as planned in the study: “HbA1c \leq 6.5% and an absence of severe hypoglycemic events at 1 year after the first islet transplant or a reduction in HbA1c of 1 point and an absence of severe hypoglycemia at 1 year after the first islet transplant “.

The DCCT trial (The_Diabetes_Control_and_Complications_Trial_Research_Group, 1993) provided the consortium longitudinal data on 711 diabetic subjects who had been under intensive monitoring of HbA1c for at least 16 months. For our purposes, we assumed that enrolled patients for this trial will undergo similar intensive insulin therapy for their diabetes (IIT) as was done in the DCCT and that a subject would be eligible for participation in CIT-06 if her/his average value of HbA1c at months 3 and 4 was greater than 7.0%. Using this criterion, 390 of the 711 DCCT subjects would have qualified. Among those DCCT patients who would be eligible for CIT-06 the observed favorable outcome rate based on 12 months follow-up was 27% (101/373, se=2.2). Since data on hypoglycemic events was not available in the DCCT data, this favorable outcome rate overestimates the true rate in the IIT group. The projected sample size will therefore be adequate. Because our patients have long standing type I diabetes and have already experienced kidney failure, it is likely that they will have more severe diabetes than those enrolled in the DCCT and that their experience with IIT will be less favorable. In addition, our information from the DCCT calculations does not include information on hypoglycemic events which was common in the DCCT patients (ref). For both of these reasons, we believe that the sample size and power calculations that are reported below are likely to be adequate.

Table 3.1 provides sample size calculations that use 27% as an estimate of the true favorable outcome rate in the IIT group. Sample sizes for alternative rates are also displayed. These were selected by using 23% (27%-2 times standard error) and 31% (27% + 2 times standard error) where the standard error is the standard error of the estimate from the DCCT study. Sample size calculations assume that an exact one sided test will be used and were calculated using the PASS (Hintze, 2011) sample size program. This table displays the sample sizes required for a one-sided 0.05 binomial test to achieve 80% and 90% power to detect true favorable outcome rates of 40%, 45%, 50%, 55%, and 60% in transplanted subjects compared to the selected rates in the IIT group. If the true favorable outcome rate at one year in IIT subjects is 27% then we would need to transplant 27 subjects to achieve 90% power to detect an improvement to 55% in transplanted subjects. We would need 19 subjects to achieve 80% power to detect 55% versus 27%. We

Statistical Analysis Plan

would need to transplant 40 subjects to ensure 90% power and 27 subjects to ensure 80% power if the true IIT rate is 31% and the true rate in islet transplant subjects is 55%.

Table 4.1: Sample sizes required to achieve 80% and 90% power

Rate in Transplanted Subjects	Power	Historic Rate - IIT		
		23%	27%	31%
40%	90%	64	113	246
	80%	46	84	175
45%	90%	39	64	105
	80%	31	46	76
50%	90%	28	39	59
	80%	21	30	43
55%	90%	21	27	40
	80%	15	19	27
60%	90%	15	19	27
	80%	12	16	17

We have chosen to transplant 24 subjects. This will provide approximately 90% power to detect a difference of 57% favorable outcome rate in islet transplanted subjects versus the estimated 27% favorable outcome rate in the DCCT population. Table 3.2 displays minimal detectable differences for sample sizes of 18, 24 and 30 subjects. With 24 subjects the smallest difference that can be detected with 90% power by a one-sided 5% level test is 57% compared to 27%. The minimal detectable difference is 52% compared to 27% with 80% power.

Statistical Analysis Plan

Table 4.2: Minimal detectable differences if the true IIT rate is 27%

	Power	
	90%	80%
18	62%	57%
24	57%	52%
30	53%	49%

Table 3.3 summarizes data provided by clinician investigators in Europe and North America. GRAGIL, CITR, and the Nordic Group reported data for HbA1c levels at one year after first transplant but did not report data on hypoglycemic events. Rates for $HbA1c \leq 6.5\%$ varied from 50% to 83.3%. Overall, 70% (33 of 47) of islet transplanted patients from the three studies reporting 12 month HbA1c values would have satisfied the HbA1c requirement for a favorable outcome one year after their first islet transplant (95% confidence interval 57% to 83%). These rates do not include those whose HbA1c levels decreases by 1% or more at one year but did not reach 6.5%. While these reports do not give the incidence of hypoglycemia in these patients, the Edmonton group has reported that the incidence of hypoglycemic events in those with a successful islet transplant is very low. The lower portion of Table 3.3 provides HbA1c data on potentially eligible subjects identified during preliminary screening at several CIT clinics. Note that the baseline HbA1c levels are similar to those from the studies that present outcome data. These data argue that we can expect to observe favorable outcome rates that are not lower than those observed by the three groups.

We expect to observe a success rate greater than 55%. The proposed IAK study has approximately 90% power to detect this difference.

Statistical Analysis Plan

Table 4.3: HbA1c levels and favorable outcomes reported by investigators in Europe and North America

Reporting Group	Occasion	Number of transplanted subjects	HbA1c % (mean±sd)	HbA1c ≤ 6.5 one year after first transplant
GRAGIL	Pre transplant	8	7.7±0.6	50% (3/6) ¹
CITR ²	Pre transplant	12	NR ³	83.3% (10/12)
Nordic Group ²	Pre transplant	29	9.0±1.7	69.0% (20/29)
	Post transplant	29	7.4±1.5	
Maffi	Pre transplant	54	8.1±1.6	NR
	Post transplant	46	7.5±1.2	
Giessen ⁴	Pre transplant	21	8.7±0.4	NR
	Post transplant	21	7.1±0.3	
HbA1c levels reported by CIT Investigators				
Edmonton	Pre transplant	8	9.3±2.0	
Pennsylvania	Pre transplant	38	8.6±1.7	
Northwestern	Pre transplant	9	6.9±1.6	
Miami, Pennsylvania, and Northwestern	Change pre transplant to 12-months post transplant	16	-1.5±1.8	

¹ HbA1c < 6.5% but hypoglycemia events not reported

² The CITR has data on 17 IAK patients who are at least one year post first transplant.

³ NR=not reported

⁴ Both IAK and SIK reported

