5.1.1 Study Period

The trial consists of three periods: (1) the pre-transplant period, which includes screening, enrollment, and wait list time; (2) the period that includes the islet transplant procedure(s); and (3) follow-up visits through 24 months following the last transplant. The study period of this trial is a 36-month follow-up after the final islet transplant. Subjects may undergo up to 3 transplants in the course of this study; the last transplant can occur not later than 8 months following the first transplant.

In the first period, individuals who meet the general inclusion criteria will be approached regarding participation in the study. After informed consent has been obtained, they will be formally enrolled into the study. Eligibility will be confirmed based on the results of the screening visit procedure detailed in Appendix 1 of the CIT-06 protocol. Enrolled subjects who meet the eligibility screening for the studies will be put on the waiting list for an islet transplant.

After completion of the screening assessments confirming eligibility for the study, a subject will undergo 12 months of intensive insulin therapy (IIT) by an experienced diabetologist (see Appendix 3). If a subject received at least 12 months of **intensive diabetes management** prior to enrollment and experienced at least one episode of **severe hypoglycemia** during that time, the subject would not be required to receive IIT while on study as long as they have a Clarke score of 4 or more. A subject is required to return to the study site for clinic visits every 3 months while undergoing IIT and while on the waitlist. Monthly HbA1c sampling between the required 3 month interval visits may be drawn locally, sent from the local lab to the study site and then shipped to the central lab for testing. Eligibility will be reconfirmed after 4 months of IIT and after 12 months of IIT. All eligibility assessments must be within the windows required for initial study enrollment. Once eligibility has been reconfirmed, a subject will be placed on the **wait list**. The subject will continue IIT while on the **wait list**.

Once a compatible islet preparation becomes available, a subject's eligibility will be re-confirmed and eligible subjects will begin immunosuppression therapy on Day -2 (Day 0 is defined as the day of transplant).

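### The 27% null rate comes from DCCT subjects selected on HbA1c above 7.0%, a rule that does not match the entry routes in Section 3, so its direction of error for the enrolled population is unknown

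*SAP*

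**What the plan says.** Section 4 derives the benchmark from DCCT subjects on intensive therapy. It assumes, for the purpose of the calculation, that "a subject would be eligible for participation in CIT-06 if her/his average value of HbA1c at months 3 and 4 was greater than 7.0" percent. The yield is given as "Using this criterion, 390 of the 711 DCCT subjects would have qualified", and among them "the observed favorable outcome rate based on 12 months follow-up was 27% (101/373, se=2.2" percent). Hypoglycemia was not in the DCCT data, and from this Section 4 concludes that 27% is too high for the IIT group. It adds that CIT-06 patients are likely to have more severe diabetes.

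Section 3 states the entry routes, pointing to inclusion criterion 7 of the protocol. A subject enters "because she/he is having severe hypoglycemic events that require assistance or because she/he is unable to reduce HbA1c level to below 7.5" percent on IIT. Of the HbA1c route it says: "The latter group may be very small". Section 5.1.1 adds that, after 12 months of prior intensive management with at least one severe episode, "the subject would not be required to receive IIT while on study as long as they have a Clarke score of 4 or more". No HbA1c value is attached to that route.

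The primary endpoint (Sections 2.3.1 and 10.1) is HbA1c of 6.5% or less, or a drop of at least 1 point, in either case with no severe hypoglycemia, at one year after the first transplant. It carries no condition on baseline HbA1c. Section 10.1 tests all subjects who begin induction against 27% with a one-sided exact binomial test at 5%.

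**The concern.** In a single-arm trial the efficacy conclusion is only as good as the external rate. Here the rate describes one population and the trial admits another. The benchmark rule removes 711 − 390 = 321 DCCT subjects (45%), those with the better early HbA1c. The hypoglycemia route as described in the SAP has no such filter, and the HbA1c route uses 7.5% where the benchmark uses 7.0%.

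The endpoint makes this matter. A subject who enters at, say, 6.3% already satisfies the HbA1c limb and needs only to stay there and be free of severe hypoglycemia. A subject between 6.5% and 7.0% needs a drop of half a point or less. If such subjects are enrolled, 27% may not be the rate they would have shown without a transplant, and rejecting 27% would be harder to attribute to the islets. The SAP's range of 23% to 31% in Table 4.1 reflects DCCT sampling error only, not this difference in population.

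**Working it through.** **Reproducing the plan.** Inputs from Sections 4 and 10.1: n = 24, null 0.27, one-sided 0.05.

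- 101/373 = 27.1%.
- P(X ≥ 10 | 24, 0.27) = 0.086 and P(X ≥ 11 | 24, 0.27) = 0.0369, so the test rejects at 11 or more, with exact size 3.7%.
- Power at 11 or more: 0.904 at 57% and 0.791 at 52%, matching the stated 90% and 80%. The arithmetic is sound. The question is whom the 27% describes.

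**How much slack the test has.** Solving P(X ≥ 11 | 24, p) = 0.05 gives p ≈ 0.282. A true no-transplant rate about 1.2 points above 27% takes the size past 5%.

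**How many candidates fall outside the benchmark.** Table 4.3 gives HbA1c for screened candidates. Assuming normality, the share at or below a cut c is Φ((c − mean)/SD):

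| Site | n | Mean ± SD | ≤6.5% | ≤7.0% |
|---|---|---|---|---|
| Edmonton | 8 | 9.3 ± 2.0 | 8.1% | 12.5% |
| Pennsylvania | 38 | 8.6 ± 1.7 | 10.8% | 17.3% |
| Northwestern | 9 | 6.9 ± 1.6 | 40.1% | 52.5% |
| Weighted by n | 55 | mean 8.4 | 15.2% | 22.4% |

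**Upward pressure.** Let f be the share of subjects outside the benchmark and q their favorable rate on IIT by HbA1c alone. The null becomes p0 = (1 − f)·0.27 + f·q. The SAP gives neither f nor q; both are assumptions.

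**Downward pressure.** Let h be the share free of severe hypoglycemia on IIT, taken as common to all subjects and independent of HbA1c (also an assumption). The null for the full composite is h·p0.

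| f | q | p0 | Size if h = 1 | h at which the null is 27% again | h·p0 at h = 0.8 | Size at h = 0.8 |
|---|---|---|---|---|---|---|
| 0.10 | 0.5 | 29.3% | 6.4% | 0.92 | 23.4% | 1.3% |
| 0.20 | 0.5 | 31.6% | 10.2% | 0.85 | 25.3% | 2.3% |
| 0.20 | 0.6 | 33.6% | 14.7% | 0.80 | 26.9% | 3.6% |
| 0.20 | 0.8 | 37.6% | 26.4% | 0.72 | 30.1% | 7.6% |

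At q = 0.27 and h = 1 nothing changes (3.7%). Plausible inputs put the true size on either side of 5%, and the SAP contains nothing that would fix f, q or h.

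**The case against.** A reader might infer that 27% is too low and that the trial's false-positive risk is therefore inflated. The document does not support that. Both limbs of the endpoint require absence of severe hypoglycemia, and the subjects most likely to be at HbA1c goal are those who enter because they have severe events. On IIT many could fail that component, and the DCCT rate makes no deduction for it. The table above shows this can bring the risk below nominal.

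A reader might also take the Northwestern figures (40% and 52%) as the trial's likely mix. They come from nine screened patients at one site. Across the three sites the mean is 8.4%, inside the 7.7% to 9.0% of the published series, so the remark "Note that the baseline HbA1c levels are similar to those from the studies that present outcome data" is fair for the average, though not for Northwestern. All the shares rest on assumed normality and on screening values, not on enrolled subjects.

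Three further points stand in the plan's favor. Section 4 presents the 7.0% rule as an assumption. Inclusion criterion 7 is in the protocol, which is not at hand, and may contain an HbA1c condition. Section 3 says only that the HbA1c route may be very small. The SAP also has analyses that bear on whether results reflect who entered: key secondary 6 (a drop of at least 1 point, which entry at goal does not confer), HbA1c change from baseline (Sections 11.2 and 13.1), and the comparisons with IIT in Sections 13.2 and 13.3.

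None of this repairs the benchmark. Those analyses do not re-derive 27% or show the primary endpoint by baseline HbA1c. The Section 3 subgroup analysis needs at least 6 subjects per route and would apply the same 27%.

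**Conclusion.** The mismatch holds on the SAP's own text: Section 4 selects the benchmark on HbA1c above 7.0%, Section 3 describes entry by severe hypoglycemia or by failure to get below 7.5%, and all induced subjects are tested against the one rate. About 22% of screened candidates (normality assumed, weighted by n) would lie outside the benchmark, about 15% of them all being already at 6.5% or less.

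The size and the net direction of the resulting error cannot be determined. One bias raises the no-transplant rate and another lowers it. Section 4 names only reasons for it to be lower, so its unqualified statement that 27% is an overestimate is not supported for the enrolled population. Inflation of the type I error is possible, because the slack is only about 1.2 points, but it is not shown. With the direction open and the entry criterion known only from the SAP's summary, this is a should-fix point.

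**What to change.** Keep the 27% primary test, and make these changes in the SAP:

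1. Reconcile the Section 4 benchmark rule (7.0%) with the Section 3 entry routes (7.5%, or severe hypoglycemia), and state how the benchmark population relates to the one enrolled.
2. Limit the claim that 27% is an overestimate to subjects with HbA1c above 7.0%. Say that for the others the bias is of unknown direction.
3. Add a pre-specified sensitivity analysis of the primary endpoint in subjects with baseline HbA1c above 7.0%. Note that even this match is approximate: the DCCT selection used months 3 and 4 of IIT, whereas trial baseline may follow 12 months of it.
4. Always tabulate the favorable rate with exact intervals by baseline HbA1c (≤6.5%, >6.5% to 7.0%, >7.0%) and by entry route, without the condition of 6 per group.

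The cost is wording and a few tables, since Section 9.1 already collects baseline HbA1c. The drawback is small subgroups and wide intervals within 24 subjects, so these results would inform interpretation and not replace the primary test.
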